10.5 Notification of deaths

All deaths will be reported to the Sponsor irrespective of whether the death is related to the IMP, or an unrelated event.

10.6 Reporting urgent safety measures

If any urgent safety measures are taken the CI/Sponsor shall immediately and in any event no later than 3 days from the date the measures are taken, give written notice to the MHRA and the relevant REC of the measures taken and the circumstances giving rise to those measures.

10.7 Development safety update reports

WCTU will prepare and submit DSURs once a year throughout the clinical trial, or as necessary to the MHRA and REC. This report will detail any new safety data received during the reporting period. The report will be submitted within 60 days of the Developmental International Birth Date (DIBD) of the trial each year until the trial is declared ended.

11. TISSUE SAMPLES

11.1 Endometrial Biopsies

Endometrial biopsies will be sent to the central laboratory at University Hospitals Coventry and Warwickshire (UHCW) and should be collected, shipped and tracked in accordance with the CERM A Manual for collection of Endometrial Biopsies.

In some women taking the endometrial biopsy can be painful and may cause cramping at the time of the biopsy. Taking Paracetamol and Ibuprofen an hour before the biopsy can help with this. If needed gas and air (Entonox) is available while having the biopsy. In some women, spotting may happen after the biopsy is taken, this will resolve quickly on its own.

11.1.1 Analysis of endometrial biopsies

Once received UHCW laboratory will set the tissue sample in a wax block for analysis. Technicians preparing the biopsies will be competent to do so by virtue of their regular clinical work and will additionally be given training in the Standard Operating Procedure for the CERM Trial.

Guidance on the laboratory processing of tissue samples can be found in the CERM A Manual for processing, staining, analysis, and reporting of endometrial biopsy samples.

Chronic Endometritis will be diagnosed based on the density of CD138 staining cells within a tissue section. This methodology was derived from previously published material³⁶ and in advance of this trial it has been externally validated for the trial by experts in the field. The endometrial sample will be embedded in paraffin wax and sectioned onto slides. The slides will be stained with CD138 mouse monoclonal antibody. These will then be reviewed and the density calculated by trained observers following a standard operating procedure to ensure consistency. Borderline samples will be counted by two observers. The process will be both internally and externally quality assured as outlined in the trial document: CERM Trial: Analysis and Reporting of Endometrial Biopsy Samples Standard Operating Procedure. A positive screen will be defined as \geq 5 CD138 positive cells per 10mm². Samples will be reported as screen positive or negative to allow progression to randomisation. Exact counts will be kept to allow sub-group analysis of the data at a later stage.

Counting will be performed by trained members of the trial team who will have undergone an extensive training presentation and will be continually quality assured both internally and externally. Borderline samples will be counted by two separate observers. Technicians will follow the CERM A Manual for processing, staining, analysis, and reporting of endometrial biopsy samples.

11.1.2 Results of endometrial biopsy samples

Biopsy results will be emailed to sites within four weeks of receipt at the central laboratory.

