1.1.8 Evidence of efficacy of doxycycline treatment

The most frequently used antibiotic regime in published studies is doxycycline (100mg twice daily for 14 days). Based on analysis of repeat endometrial biopsies, a single course of doxycycline was reported to 'cure' histologically defined CE in 92%,⁹ 94%¹² 75%,¹³ and 70%¹⁴ of patients. Following doxycycline treatment, changes to the endometrial microbiome have been identified. Notably, the detection rates of Corynebacterium, Enterococcus, Escherichia coli, Streptococcus agalactiae, Ureaplasma urealyticum and Ureaplasma parvum were significantly lower following antibiotic treatment.⁹ This reduction in pathogenic microorganisms was associated both with a significant increase in Lactobacillus spp, the major resident species within the uterine cavity³⁰ and a reduction in the number of plasma cells within the endometrial stromal compartment.⁹ This suggests a shift towards a normal microbiota following doxycycline treatment. Importantly, no trial to date reported on the persistence of CE on repeat biopsies in non-treated women. We found that \geq 12 CD138+ cells/mm2 persisted in only 78% of untreated women when biopsied again after two or more cycles (n=32).

These observations suggest that CE may resolve spontaneously, or be intermittent, in some women but persists in others. Further, in addition, to its antibacterial properties, doxycycline has a well-documented anti-inflammatory effect,³¹ raising the possibility that it is useful for the treatment of CE not associated with endometrial symbiosis.

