CERM B patients will all be recruited at University Hospital Coventry and Warwickshire NHS Trust. CERM B patients will follow the same pathway as CERM A patients but will have the following additional assessments:

- Patients will be registered into the screening trial, consented to the CERM B trial and have a vaginal, endometrial and cervical swab at registration.
- Women who screen positive for CE and are randomised into the trial will have a second endometrial biopsy following treatment.
- Women who screen positive for CE and are randomised into the trial will have a second vaginal, endometrial and cervical swab following treatment.

In order to analyse if doxycycline treatment improves CE and microbiota composition 200 paired endometrial biopsy and endometrial swab samples are required from patients before and after treatment. Approximately 400 patients will be registered into CERM B and have the additional vaginal, endometrial and cervical swab at registration. Approximately 200 of these patients will screen positive for CE and be randomised into the trial. These patients will have the repeated endometrial biopsy and vaginal, endometrial and cervical swab following treatment. A random sample of vaginal and cervical swabs will be analysed to ensure no contamination of the endometrial swab sample.

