7.6.2 Consent to participate in the RCT CERM B

Women attending the UHCW site will be asked to consent to the CERM B RCT. These participants will consent to having a second endometrial biopsy and vaginal, endometrial and cervical swabs being taken.

Following consent the site research team should ensure that participants have been given a copy of the signed CERM B RCT informed consent form and PIS.

Screen-positive women in CERM B will have a biopsy during the luteal phase (10 ± 4 days) after ovulation during the intervention cycle. CERM B participants should be provided with a second biopsy preparation kit. The preparation, procedure and analysis will be identical to the first biopsy procedure (see the tissue samples section of the protocol for further details).

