7.8 Blinding

The trial is a double blind trial the participants, clinicians, pharmacist or the research team do not know the treatment allocation. All drug packs containing either doxycycline or placebo will have an individual pack number but are otherwise identical. Unblinding is possible if clinically necessary (figure 3).

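### The biopsy-reporting rule does not exclude the CERM B post-treatment biopsy; read literally, it gives the UHCW site team a partial read-out of treatment arm in about 200 women

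*Protocol*

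**What the plan says.** Section 11.1.2 consists of one sentence: "Biopsy results will be emailed to sites within four weeks of receipt at the central laboratory". Section 7.5 gives the same four-week turnaround, in the part of the protocol that runs from registration to randomisation.

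Section 4 adds a second biopsy for the CERM B subset, all at UHCW: "Women who screen positive for CE and are randomised into the trial will have a second endometrial biopsy following treatment". On numbers it says "Approximately 200 of these patients will screen positive for CE and be randomised into the trial". Section 7.6.2 places this biopsy in the luteal phase of the intervention cycle, says "The preparation, procedure and analysis will be identical to the first biopsy procedure", and sends the reader to the tissue samples section, which is section 11.

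Section 7.8 promises that "the participants, clinicians, pharmacist or the research team do not know the treatment allocation".

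Two places bear on what was intended. Section 11.1.1 gives a purpose for reporting: "Samples will be reported as screen positive or negative to allow progression to randomisation". Table 5 schedules telling the woman her CE result once only, after registration.

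Section 11.2.1 does protect the blind for the microbiome laboratory, which learns allocation only when the trial ends. No matching sentence covers the CD138 result.

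**The concern.** The first biopsy result is needed for eligibility. The second leads to no decision in the trial, and it shows whether CE has responded to treatment. If doxycycline works as the background section suggests, a cleared biopsy points to doxycycline and a persistent one to placebo.

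The timing is unhelpful. The second biopsy is taken 10 ± 4 days after ovulation in the treatment cycle. Assuming ovulation on day 14 of a 28-day cycle and prompt receipt, that is day 20 to 28. A result up to 28 days later arrives by about day 48 to 56, or seven to eight weeks after the first capsule. The sample-size section expects the 12-week outcome 16 to 36 weeks after randomisation. The same site team then telephones randomised women every three months (9.5.2) and records their pregnancies.

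Two things are at stake. The first is the blind of the staff who follow these women. The second is contamination: if the result were passed on, mostly placebo women would hear that CE persists, and section 1.1.2 notes that antibiotics for CE can be had privately. That would pull the comparison towards no difference.

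**Working it through.** **Inputs**
- Cure on doxycycline, c (section 1.1.8): a single course was "reported to 'cure' histologically defined CE in 92%,⁹ 94%¹² 75%,¹³ and 70%¹⁴ of patients".
- Persistence untreated, p (section 1.1.8): CE "persisted in only 78% of untreated women when biopsied again after two or more cycles", n=32, at a cut-off of 12 or more CD138+ cells/mm².
- Allocation 1:1 (750 and 750) and target 48% v 56% (section 12.1.3).
- About 200 randomised CERM B women (section 4).

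**The protocol's own figure.** 25/32 = 78.1%, so the 78% reproduces. The protocol gives no figure for guessing the arm.

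**Share guessed correctly.** Take cleared as doxycycline and persistent as placebo. Under 1:1 allocation the share correct is (c + p)/2. The predictive values are:
- P(doxycycline | cleared) = c/(c + 1 − p)
- P(placebo | persistent) = p/(p + 1 − c)

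With p = 0.78:

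| c | Correct | Of 200 | P(dox, cleared) | P(placebo, persistent) |
|---|---|---|---|---|
| 0.70 | 74.0% | 148 | 0.76 | 0.72 |
| 0.75 | 76.5% | 153 | 0.77 | 0.76 |
| 0.92 | 85.0% | 170 | 0.81 | 0.91 |
| 0.94 | 86.0% | 172 | 0.81 | 0.93 |

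Chance is 50%, or 100 of 200.

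**Sampling error in p.** The exact 95% interval for 25/32 is 60.0% to 90.7%. The lowest case is (0.70 + 0.600)/2 = 65%. The highest is (0.94 + 0.907)/2 = 92%. This leaves out sampling error in the cure rates, for which the protocol gives no denominators.

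**Cut-off.** Twelve cells per mm² is 120 per 10 mm². The trial counts 5 or more per 10 mm² as positive. As printed, the two differ by 120/5 = 24-fold. The protocol gives neither clearance nor persistence at the trial's cut-off.

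**Extreme case for the main comparison.** About 100 of the 200 women are on placebo. At 78% persistence, 78 have a persistent result, which is 78/750 = 10.4% of the placebo arm. If all 78 took off-trial treatment and each gained the full 8 points, the placebo rate would rise by 0.104 × 8 = 0.83 points. The difference would fall from 8 to about 7.2 points. At an assumed 25% uptake the shift is about 0.2 points. If the 8-point average gain arose only in women whose CE would persist, the gain per such woman would be 8/0.78 = 10.3 points and the shift 0.104 × 10.3 = 1.1 points, still small.

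**The case against.** The strongest reply is that 11.1.2 was written for screening. Section 11.1.1, just before it, ties reporting to progression to randomisation, and a post-treatment biopsy leads to no randomisation. Section 7.5 sits in the screening pathway. Table 5 has no entry for informing the woman of a second result, and 9.4.1 lists the second-biopsy visit with no result step. Section 7.6.2 makes preparation, procedure and analysis identical but does not mention reporting. Section 11.1.1 also leaves reporting detail to an operating procedure and a manual that are not shown, and these may already withhold the second result.

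Most of this stands as evidence of intent. A reader might infer that the protocol orders every biopsy result to be sent to the site; it does not say so. But none of these passages forbids the release. Table 5 concerns the woman rather than the site, and a laboratory working from 11.1.2 alone could send the result in good faith.

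It is also fair to say that the guess is probabilistic. On the figures above, 19-24% of cleared results and 7-28% of persistent results would mislead. The primary outcomes (fetal heartbeat at a set crown-rump length, and live birth) are largely objective. The contamination route needs two further steps, disclosure and private treatment, and the protocol schedules neither.

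**Conclusion.** The point holds as a gap in the reporting rule, of moderate severity. As written, the protocol does not stop a treatment-response result from reaching the UHCW team in about 200/1,500 = 13% of randomised women, and this sits badly with 7.8.

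On the background figures, the arm could be guessed correctly in about 74-86% of these women, or 65-92% with sampling error in the 78%. These figures assume that background cure and persistence carry over to the trial's cut-off and to a biopsy in the treatment cycle. The protocol does not support that assumption, so the true share is unknown.

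A reader might go further and conclude that the site is outright unblinded, or that the live-birth comparison is seriously biased. The documents support neither. The result gives odds, not the allocation, and the extreme contamination case costs about 0.8 of 8 points. Any effect through follow-up or reporting by unblinded staff is not quantified here, but it is confined to one site and to largely objective outcomes.

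**What to change.** - Limit 11.1.2 and 7.5 to the screening biopsy.
- State that CD138 results of the second CERM B biopsy go only to the Warwick Clinical Trials Unit database. Withhold them from participants, and from UHCW staff who manage or follow up randomised women, until the woman's follow-up is complete.
- Keep laboratory staff and counters who see second-biopsy results separate from that follow-up. The central laboratory is at UHCW (11.1) and counting is done by members of the trial team (11.1.1), so changing the email list alone would leave a route open.
- Say this in the CERM B RCT information sheet, and bring the reporting procedure into line.

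With the result withheld, a guess from this source falls back to 50%. The cost is a few sentences and a change to laboratory reporting. The real downside is waiting time: with 24 months of recruitment (12.1.3) and 14 months of follow-up after the last randomisation (7.11), an early recruit who does not conceive could wait up to 24 + 14 = 38 months for her second result. The information sheet should tell women this.

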11.2 Microbial swabs

For participants registered for CERM B a microbial swab of the vagina, endometrium and cervix will be taken and sent to Imperial College London for analysis in special containers.

Clinicians taking swabs will be competent to do so either by virtue of clinical role and training or appropriate specialist training on the technique for the trial. Clinicians will follow the CERM B Manual for collection of Microbial Swabs.

11.2.1 Analysis of the microbiome

Vaginal, endometrial and cervical swabs before and after treatment will be sent to Imperial for exploratory analysis of the endometrial microbiome. These paired samples will be labelled with:

- Trial ID number
- first or second sample
- Treatment allocation Imperial researchers will only be told treatment allocation at the end of the trial.

Details of the preparation of the swabs and analysis is in the SOP for microbiome analysis. Microbiologists undertaking the analysis of swabs will be doing so commensurate with their role having previously undergone relevant training in the area.

In some cases there may be tissue left over, with the women's permission, we will keep this tissue for future research studies into pregnancy loss. The tissue will be stored anonymously in the Tommy's reproductive health bio-bank and kept strictly in accordance with The Human Tissue Act 2004.

12. STATISTICS AND DATA ANALYSIS

12.1 Sample size

12.1.2 Sample size – screening trial

The target sample size for the screened participants is 3,062.

12.1.3 Sample size - randomised controlled trial

The target sample size is 1,500, 750 women in the intervention arm (doxycycline) and 750 women in the control arm (placebo).

The total number of women recruited to the screening part of trial will be determined by the proportion eligible for the randomised controlled trial. Our current assumptions suggest as overall recruitment of around 3,062 women over 24 months with 1,500 women in the randomised trial.

In simulations, we have used a maximum sample size of 1,500, and a maximum recruitment rate of 16 women/week from all centres. We have used four interim analyses, after 250, 500, 750 and 1000 women have been recruited, with the following stopping rules: stopping for futility/harm if the predictive probability of obtaining p<0.025 if the trial continued to its full sample size is less than 0.01, and stopping for established efficacy if the probability that the intervention is better than control is greater than 0.99. We assumed that 24% of women would get pregnant every month, giving an overall proportion achieving pregnancy by six months of 80%, and that the 12-week outcome would be known between 16 and 36 weeks after randomisation. The performance of this design was good in two treatment effect scenarios. With no difference between the intervention and control groups, 71.4% of trials stopped early for futility (correctly), and 1.2% stopped early for success (Type I error). The average sample size was 1193, and the average duration was 130 weeks (recruitment and follow-up). With the target treatment effect (48% control, 56% intervention), 54.8% stopped early for success, and an additional 33.4% did not stop early but found probability of benefit to the intervention group of >95%, giving an overall probability of correctly identifying benefit (power) of 88.2%. Average sample size was 1,247 and duration was 133 weeks.

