Smoking history		•								
Medical History		•								
Concomitant medication review		•		•						
Obstetric History		•								
Pregnancy History		•								
Review Eligibility		•		•						
Pregnancy Test		•		•	3					
Contraception use review		•		•	•					
Period Review		•		•	• 3					
Written Consent Screening CERM A or CERM B ³		•								
Registration		•								
Endometrial Biopsy			•		3					
Swabs – CERM B Only ³			3		• 3					
Inform patient of CE results			•							
Adverse event review				•	•	•				1
Written Consent Randomisation ²				•						
Randomisation				•						
Treatment instructions				•						
Dispense medication				•						

The CERM trial Protocol

Treatment compliance check			•					
Contact patient every 3 months to determine pregnancy				•				
Pregnancy confirmation					•	• 4		
Ultrasound					•	•	6 5	
Concomitant medication review (on trial)			•		•	•	•	•
Pregnancy complications ⁴					•	•	•	•
Pregnancy outcome assessments								•

¹Verbal consent must be given (and documented) prior to biopsy kits being given/sent

²Written informed consent must be given prior to any trial specific procedures taking place.

³CERM B patients only (UHCW ONLY)

⁴ If appropriate

⁵Only if clinically indicated

⁶Timing of visit as per local hospital policy

Table 6 – Trial tasks and Milestones

Tasks	Time period (months)
Trial preparation: approvals (ethics, R&D), research governance (oversight committees (TMG, TSC and	⁻ 2 - ⁻ 1 (pre-start)
DMC), staff training), develop project management plan, registration, contracting, new appointments,	
send capacity and capability questionnaires to trial sites, trial administration processes (participant files,	
master file), trial branding, and social media.	
Trial set-up: liaise with trial pilot sites, track R&D, develop randomisation service, develop data collection	1 - 3
process, prepare training manual, print recruitment information (introduction letter, participant	
information sheet, participant information leaflet, posters) and prepare site-initiation materials.	
Site set-up: Initially ten sites; four per month (not including the first and last months, August and	4 - 22
December).	
Participant recruitment: n=1,500 randomised	5 -30
Feasibility: after six months when >68 participants have been recruited.	Around 10
Follow-up: birth.	7 - 38
Interim analysis: when data on primary outcome on n=250, 500, 750, 1,000 available.	Around 9-21
Data analysis	36 - 40

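### The 1.2% labelled Type I error counts only false positives at the interim looks, while the 88.2% power also counts successes at the final analysis

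*Protocol*

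**What the plan says.** Section 12.1.3 describes a simulated adaptive design with up to 1,500 women, 750 per arm. Its looks are set out as follows: "We have used four interim analyses, after 250, 500, 750 and 1000 women have been recruited". Table 6 times them differently, "when data on primary outcome on n=250, 500, 750, 1,000 available".

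The rules are:
- Futility or harm: stop if the "predictive probability of obtaining p<0.025 if the trial continued to its full sample size is less than 0.01".
- Early efficacy: "stopping for established efficacy if the probability that the intervention is better than control is greater than 0.99".
- Final success: no separate rule is given. The bar appears only in the power sentence, where "an additional 33.4% did not stop early but found probability of benefit to the intervention group of >95" per cent.

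With no difference, 71.4% of simulated trials stopped for futility and "1.2% stopped early for success (Type I error". With 48% against 56%, early successes (54.8%) and final successes (33.4%) are added to give power of 88.2%. Section 12.3.1 repeats these results. Neither section gives the share of null trials that crossed the final bar, or a total Type I error.

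**The concern.** A trial that runs to 1,500 women and crosses the final bar counts as a success when the treatment works, so it must count as a false positive when the treatment does not work. The paragraph does the first and omits the second, yet calls the remaining part Type I error.

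The two figures stand next to each other in support of the statement that the design performed well, and a reader will take 1.2% and 88.2% as a pair. They are not on the same definition. This matters because section 17 expects rapid uptake into practice if benefit is shown, so the chance of a false positive is a property that the sponsor, funder, ethics committee and DMC need stated correctly.

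**Working it through.** **From the printed figures alone.** Power: 54.8% + 33.4% = 88.2%, as stated. Null trials stopping early: 71.4% + 1.2% = 72.6%. Null trials reaching the final analysis: 100% − 72.6% = 27.4%. The 1.2% could be the whole Type I error only if none of that 27.4% ever crossed the final bar.

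**Size, by simulation.** Inputs from 12.1.3: looks at 250, 500, 750 and 1,000; final analysis at 1,500; 48% v 48% under the null and 48% v 56% under the target effect; futility cut-off 0.01. Flat priors are assumed.

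The test statistic Z is followed at information fractions t = 1/6, 1/3, 1/2, 2/3 and 1. Its mean at the end under the target effect is 0.08 / √[(0.48×0.52 + 0.56×0.44)/750] = 3.11. With a flat prior, the predictive probability of final significance is Φ[(Z − c√t)/√(1−t)], where c is the critical value for p<0.025: 1.96 if one-sided, 2.24 if two-sided. Efficacy stops occur at Z > 2.326 (probability 0.99) or Z > 2.576 (0.995). Final success is Z > 1.645 (0.95) or Z > 1.96 (0.975). There were 2,000,000 runs per scenario.

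| Reading | Null: futility | Null: early + final = total | Target: early + final = power |
|---|---|---|---|
| Protocol as printed | 71.4% | 1.2% + not given | 54.8% + 33.4% = 88.2% |
| A. Two-sided (0.995/0.975), futility two-sided | 71.2–71.4% | 1.4% + 1.9% = 3.3% | 54.1% + 33.3% = 87.4% |
| B. Printed (0.99/0.95), futility one-sided | 63.2% | 2.7% + 3.6% = 6.3% | 64.3% + 28.4% = 92.7% |
| C. As B, but 1,200 evaluable (80% of 1,500), futility two-sided | 71.2% | 2.7% + 3.5% = 6.2% | 54.3% + 32.1% = 86.5% |
| D. Hybrid (0.995/0.95), futility two-sided | 71.3% | 1.4% + 4.0% = 5.4% | 54.2% + 37.7% = 91.8% |

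Totals are rounded from unrounded components.

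**Which reading fits.** A comes close to all the printed percentages. Patient-level runs of A, with the 16 to 36 week outcome lag and looks timed by available data, give average sample sizes of 1,198 and 1,246 (printed: 1,193 and 1,247) and a total false-positive rate of 3.6%. C also comes within 2 points on futility and power, but gives 2.7% early false positives. The printed percentages are all multiples of 0.2%, which would fit about 500 runs (an inference). With 500 runs, seeing 1.2% or less has probability 0.02 if the true rate is 2.7%, and 0.44 if it is 1.4%. This favours A but does not prove it.

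**Plausibility check on A.** About 1.9/27.2 = 7% of null trials that reach the end then cross the bar. Applied to the printed figures: 1.2% + 27.4% × 0.07 = 3.1%.

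**Other variants.** A separate simulation of 600,000 null trials gave 3.4% for the two-sided reading and 6.5% at the printed thresholds. If success is judged on all randomised women, including about 410 with outcomes pending (an assumed number), the totals are 2.8% and 5.5%. Changes to look timing and evaluable number moved the printed-threshold total between about 6.0% and 7.5%, mostly 6.1% to 6.8%. Thresholds stricter than either reading (0.9975/0.99) gave about 1.8%, with power of only about 78%. They are not readings of this protocol, and even they exceed 1.2%.

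**The case against.** The strongest reply is that the sentence never says the overall error is 1.2%. It says these trials stopped early, its brackets can be read as classifying each kind of early stop (one correct, one an error), and only power is called overall. That is a fair reading, and no sum in the paragraph is wrong. The fault is therefore a misleading label and a missing total. The label still attaches the name of an operating characteristic to part of it, beside a power figure counted in full.

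A second reply is that the size is uncertain. It is. As worded, the 0.99 and 0.95 thresholds are one-sided, and the two-sided reading is inferred from the outputs. Its fit is close, not exact (1.4% against 1.2%, 87.4% against 88.2%). This limits what can be said about the amount, not about the omission.

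Three stronger inferences are tempting, and the protocol supports none of them:
- That the true error is a fixed multiple of 1.2%. This would divide results from several assumed rules by one output of a simulation that is not shown.
- That the design breaches a 2.5% limit. The protocol sets no overall alpha; p<0.025 appears only inside the futility rule, without sidedness, and a final bar of 0.95 could equally suggest a nominal one-sided 5%.
- That the final bar must be raised. That would be a design change with a cost in power, and nothing here requires it.

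A statistical analysis plan may report the total error, but that would not correct the label printed twice in the protocol.

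**Conclusion.** The point holds as one of labelling and incomplete reporting. The text alone shows that 1.2% is the early-stopping share, that power includes final-analysis successes, and that 27.4% of null trials reach a final analysis whose false positives are not counted.

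The size is conditional on the rule. The one-sided total is about 6.2% to 6.5% at the thresholds as printed and about 3.3% to 3.4% on the inferred two-sided reading. Across the main readings it runs from about 2.8% to 6.5%, and look timing can take the printed rule somewhat higher. These figures assume flat priors, 48% in both arms and stopping rules followed exactly. Confidence is high that 1.2% is not the total, and moderate about which total applies.

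**What to change.** In sections 12.1.3 and 12.3.1:
1. Relabel 1.2% as the rate of early stopping for success under no difference, and remove the Type I error label from it.
2. Print the total Type I error, early plus final, from the sponsor's own simulation for the rule adopted, with the final-analysis share shown separately as is done for power. The figures above should not be copied in, because they rest on assumed rules.
3. State whether each of the 0.99, 0.95 and p<0.025 thresholds is one-sided or two-sided, and give the final success criterion as a rule instead of leaving it inside the power sentence.

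The cost is a few lines of text and one less favourable stated figure. Sample size, looks and final bar can stay as they are. Whether the restated total is acceptable is then for the sponsor and the oversight committees to judge.
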